Potential Risks. Nausea, vomiting, weakness, dizziness, and rapid heartbeat occur rarely and are most often caused by continuing to smoke while using the patch. If these reactions occur, and the participant is currently smoking and using the patch (i.e., the participant has lapsed but still is wearing the patch), participants will be counseled to reestablish a target quit day and gradually reduce their smoking rate. Participants will not be instructed to discontinue their patches if they have lapsed unless a serious adverse event has occurred, because research indicates that: 1) continuing patch use even when a lapse to smoking has occurred can increase the probability that recovery to abstinence will occur [125]; 2) high doses of nicotine, including 63-mg doses, do not lead to serious adverse events even with concurrent smoking [126]; and 3) patch use prior to a designated target quit day and with concurrent smoking does not lead to serious adverse events and can increase the chances for successful cessation [127]. Such findings have led to a general reconceptualization of the issue of concurrent tobacco and nicotine patch use in which smokers are now advised to continue nicotine patch use even if they have lapsed following a target quit day [128]. Some individuals who use the patch experience minor skin irritation, such as redness, rash, or minor swelling, and insomnia and dream abnormalities. Insomnia and dream abnormalities can be resolved by removing the patch during the night while sleeping. All of these reactions cease once the patch is removed. The EEG assessment carries the minor risk of skin irritation from the electrolytic solution, although this reaction is rare and easily treated. It is unlikely that completing the questionnaires, the attentional bias assessment, or the attentional bias modification task would lead to any potential risks for participants. In the event that an individual's response to a questionnaire indicates that there may be a mental health concern, staff will contact a mental health assessor and follow established procedures for handling mental health emergencies.

Table 1. Inclusion/Exclusion Criteria.

Inclusion Criteria

- Age: 18-65 year old.
- Smoking: an average of 5 or more cigarettes or little cigars per day prior to phone screen.
- Expired carbon monoxide (CO): ≥ 6 ppm or NicAlert >2.
- Having a working telephone.
- Seeking smoking cessation treatment.
- Fluency in spoken and written English.
- Must sign the picture consent form.

Exclusion Criteria

- Taking psychotropic, anticonvulsive, or narcotic medication.
- Unwilling to alter or remove hairstyle, hair extensions, or wig during the clinic visits to allow for correct EEG sensor placement.
- Meet criteria for a current major depressive episode or suicidality.
- Has a history of neurological illness or closed head injury
- Reports diagnosis of seizure disorder.
- Uncorrected vision problems.
- Involved in current smoking cessation activity.
- Testing positive on a urine drug screen for drugs of abuse/potential abuse.
- Women who are pregnant or breastfeeding.
- Shares the same address as a currently enrolled participant.
- Unwilling to use NRT.
- Considered by the investigator to be an unsuitable or unstable candidate (e.g., due to cognitive impairment).

2. Adequacy of Protection Against Risks

Recruitment and Informed Consent. Participants will be recruited from the Houston community by using one or more of the following means: mail, public service announcements, media interviews, MD Anderson Internet, newspaper advertisements, MD Anderson Conquest Magazine, and advertisements and mailers from the MD Anderson community liaison and outreach offices sent to all affiliated providers on the mailing list. The Tobacco Research and Treatment Program's web screener database for tobacco users, outlined in IRB-approved PA18-0423, also may be used as a recruitment source for this study. This database houses data collected from an internet-based screening questionnaire (See Appendix ZZ) to recruit tobacco users from the Houston area, as well as across Texas more broadly, who may be interested in participating in tobacco use and cessation studies at MD Anderson Cancer Center. PA18-0423 allows the sharing of data with IRB-approved MD Anderson protocols. Verbal consent will be obtained and documented before the telephone screening, and written consent will be obtained at onset of the orientation interview, where the participant will sign both the Informed Consent Document and the Picture Consent Form (See Appendix). Participants will be provided with a detailed description of the study, information about risks, and their right to withdraw from the study.

Protection Against Risks.

NRT is an FDA approved medication for smoking cessation. We will use an 8 week course of NRT as described in our methods. Moreover, we will also provide smoking cessation counseling consistent with the Clinical Practice Guidelines for Smoking Cessation.

The typical side effects of the nicotine patch are not usually serious in nature. Adverse effects will be assessed at each of the post-baseline laboratory and counseling sessions. In the event of a SAE being reported, a member of the medical team will be consulted. The SAE will be documented and reported according to institutional guidelines. The Tobacco Research & Treatment Program (TRTP) has trained medical personnel on staff that will be available to assist the PI and other personnel in managing medically related study issues.

Confidentiality will be protected by identifying subjects only by numbers in all data files. Identification numbers will only be connected to individual participant names in a separate file that will be accessible only by the PI and his staff. All study data files will be server-maintained with limited access by using passwords and logins restricted to study staff. All information will be reported in aggregate form, and individual participants will not be identified in any public reports or documents. We expect these procedures to be highly effective for protecting participant confidentiality.

3. Potential Benefits of the Proposed Research to Participants and Others

A primary benefit to participants in the proposed study is smoking cessation. All participants will receive empirically validated treatments for smoking cessation, concurrent NRT and smoking cessation counseling. We anticipate that many of them will continue to be non-smokers after the completion of the study. Smoking cessation is important in cancer prevention, cardiovascular events and emphysema rate reduction therefore reducing medical costs, and increasing well-being for both the participants and society in general. Smoking cessation is cost effective and results in a substantial reduction in healthcare costs for both the individual and society.

4. Importance of the Knowledge to Be Gained

At the conclusion of this project, we anticipate that our study will have a positive impact on smoking cessation treatment by identifying an innovative low-cost non-pharmacological intervention that alters AB and smoking behavior and that could be used as an adjunct with current first-line cessation therapies. Given the high relapse rates of smokers who receive first-

line therapies, greater than 70% by 6 months post-quit [1], alternative and complementary smoking-cessation therapies are needed that focus on reducing the salience of smoking cues that activate neurobiological signals associated with smoking behavior. An effective but low-cost intervention like ABM offers the potential to decrease relapse rates by focusing directly on a neurobiological process that may place smokers at greater risk for relapse as they encounter smoking cues in the natural environment. The significant potential benefits that would accrue with increased effectiveness in smoking cessation will far outweigh the minor risks associated with the proposed research.

5. Data And Safety Monitoring Plan

The IRB of The University of Texas MD Anderson Cancer Center reviews and approves the Data and Safety Monitoring Plan for all clinical trials. This study will be monitored for safety by the PI and co-investigator or by the institutional Data Monitoring Committee (DMC) as determined by the IRB during their review of the protocol. Plans and procedures for maintaining data integrity, defining and reporting AEs/experiences, and IRB oversight and monitoring of this project (including monitoring of participant eligibility and accrual, AEs, and interim data analyses) are described below. The procedures for IRB monitoring are described in a separate section below, followed by sections defining and further describing procedures for reporting AEs and procedures for ensuring data quality and integrity. All data will be stored in the Tobacco Research and Treatment database (APPID-264846).

IRB Monitoring

During the protocol review-and-approval process, the IRB determines the level of safety monitoring required for each protocol. The minimum monitoring requirements for low-risk trials include investigator monitoring of participant safety, AE reporting in compliance with IRB, NIH, and FDA guidelines, and participation in the Continuing Review process with the IRB. All other trials may also be monitored by the DMC. Outcomes of IRB and DMC reviews are conveyed to the PI via the administrative support staff in the Office of Protocol Research (OPR).

Guidelines for Filing Reports of Adverse Events at MD Anderson Cancer Center

We anticipate that when an AE occurs, it will be associated with NRT application site reactions, the most frequent adverse events associated with NRT. The use of the electrolytic solution for EEG collection might cause temporary skin rash in sensitive participants. Soon after removal of the EEG net, the skin redness disappears and does not result in serious adverse health consequences.

Adverse Events Requiring Prompt Reporting

Internal Serious Adverse Events (SAE) that are unexpected (not listed in the Informed Consent Document) and are related (possible, probable and definite) must be reported to the IRB within 5 working days. Deaths that are related and occur within 30 days after completion of treatment must be submitted to the IRB within 24 hours. Adverse events not meeting these criteria will be reported to the IRB at Continuing Review according to IRB policy.

Serious Adverse Event

A Serious Adverse Event is an event that meets one of the following: results in death, is life-threatening, results in hospitalization, results in persistent or significant disability/incapacity, results in a congenital anomaly/birth defect, based upon appropriate medical judgment, or may jeopardize the subject's health and may require medical or surgical intervention to prevent one of the other outcomes listed in this definition.

Data Quality and Integrity

Because of the ongoing monitoring of the project, study investigators and staff are responsible for ensuring that data quality assurance procedures are developed and maintained. Several procedures will be used to maintain the integrity of the data. All databases will be stored in a centralized location on one of the departmental servers, which is backed up daily, with access limited to specific users at the discretion of the PI. The PI will assure that audits of selected subsets of data are performed and that appropriate safeguards of participant privacy are maintained. Privacy safeguards will include appropriate password protection and physical security for all computer systems.

Additional quality assurance procedures include a data collection protocol documented in a protocol manual; a two-stage editing procedure for survey data collection consisting of the initial review of the data collection form by a project member immediately following data collection, and a second review by a project member who will record any significant deviations from the protocol; and regular meetings between the study statistician, the PI, data managers, and other project staff to review problems and solutions, and discuss concerns. Data entry systems, whether via a CATI, or QDS, system, scannable forms, or hand entry with verification, specifically provide field checks, range checks for continuous variables and valid value checks for categorical variables; checks for legitimate dates and times and logical consistency. During data collection, we will issue reports weekly, or even following any new data entry, depending on the needs of the project. Queries and reports will be provided to the PI. Preliminary review will be initiated shortly after data collection begins to allow monitoring of data quality.

F. INCLUSION OF WOMEN AND MINORITIES

Inclusion of Women

Women will comprise approximately 50% of the targeted sample. In our previous research, we encountered no difficulty in recruiting women participants.

Inclusion of Minorities

According to the U.S. Census Bureau (2010), the population of the Houston community from which the sample will be drawn (including Harris County) is estimated at 4,070,989 people. The ethnic distribution has been reported as 73% white (35% of whom are not of Hispanic origin), 19% African American, 6% Asian, and 40% Hispanic or Latino (of any race). We expect to recruit minority smokers in proportion to the population demographics and CDC 2009 smoking prevalence. We have had good success in recruiting from ethnic minority populations, especially African Americans, across all of our studies. Our success with Hispanic smokers has been more modest, although it must be noted that smoking rates are lower in the Hispanic and Latino community compared with rates in the non-Hispanic community.

If needed, we may also attract minority smokers to the proposed study by using direct public service advertisements targeted to minority smokers on Houston radio stations and newspapers supporting a large minority audience. Houston has two television stations and several radio stations and newspapers that serve the Hispanic community. The Office of Public Affairs at MD Anderson has also agreed to assist us by arranging for our participation in institution-wide cancer prevention outreach programs directed at the Hispanic community. Such events are sponsored several times a year in areas of the community with high concentrations of minority Houstonians. We will focus additional recruitment effort on these venues to increase our recruitment of Hispanic smokers. Such efforts will be in addition to the normal interviews, advertisements, and news releases conducted on our behalf by the Office of Public Affairs at MD Anderson.

G. INCLUSION OF CHILDREN

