One unpublished study has demonstrated the feasibility of administering an in-home ABM intervention in smokers that alters AB to smoking cues [49]. In this preliminary study, smokers not interested in quitting (n=60) were randomly assigned to complete 3 ABM or 3 sham training sessions per day and 1 AB assessment per day for a week. The training and assessment was a MDP task administered through a personal data assistant (PDA) hand-held computer. The participants completed 71% of the training sessions, with no differences in completion rates by intervention group. There was a significant group by time interaction, such that smokers in the ABM training group demonstrated reduced AB to smoking cues over time compared to those in the sham training group. However, neither smoking behavior, long-term changes in AB, stimulus generalization of ABM effects to other AB modalities, nor ERP measures of AB were assessed in this study, all of which we intend to evaluate with this proposed grant project.

ERP measure changes in AB. ERPs provide a multidimensional measure of the components of attention processing. ERPs are EEG signals that are time-locked to the onset of

Figure 1. The temporal location of the P1 ERP component.

a stimulus or response, and then averaged over many trials to provide waveforms whose time course has been associated with stages in the attention spectrum, from sensory to evaluative processes [50]. While both RT and ERPs are sensitive to AB, ERPs' temporal resolution provides an advantage for examining early attentional processes that RT cannot duplicate. One ERP component in particular, the P1, has been helpful in studying AB (Figure 1). The P1 component is thought to be influenced by location of the stimulus with respect to the subject's spatial attention [51]. The generators of the P1 are primarily located in the occipital areas of the brain, peaking within 90 to 160 ms from visual stimulus onset [52]. Several studies demonstrate the sensitivity

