occurs in place of one them until a button is pressed, or until 1000 ms has passed. Participants will be instructed to press a button corresponding to the side of the screen (left or right) where the probe appears. Incorrect responses, or responses that occur outside of 20-1000 ms interval after probe onset, will result in the word "incorrect" appearing on screen in red for 2000 ms. The laboratory AB assessment will consist of 16 picture pairs repeated 10 times over four blocks, for a total of 160 trials. Every picture pair will be probed, with random probes following each picture or word an equal number of times, and each picture or word randomly located on the left and right of the screen equally often. After each block of 40 trials, participants will receive feedback on their performance, including accuracy and mean RT, and be instructed to relax for 20 s before the start of the next block. An on-screen tally of money earned and lost will also appear as part of this feedback, with participants gaining \$0.025 for each correct response within the response window (\$4 maximum). An AB score will be calculated by taking the mean RT difference between the CIG and NEU targets on trials with correct responses within the response window [7,91]. As part of the exploratory data analyses, participants' eye movements will also be tracked using the Tobii TX-300 eye tracking system developed by Tobii Technology, Inc. during a paired picture-viewing task. Eye movement data will be used to supplement RT data collected during the MDP, because recent studies of attention-bias for both alcohol [92] and tobacco [93] use disorders have called into question the reliability of reaction time as the primary outcome measure of AB. Laboratory sessions, including smoking behavior and ERP assessments, will be conducted by a laboratory technician and overseen by PI [name], and co-I [name], experts in using electrophysiology to study attentional and affective processes. The laboratory AB assessment will last approximately 10 min. Prior to beginning the first MDP task, the Self-Assessment Manikin (SAM) will be administered to allow participants to rate the images used in the experiment on the dimensions of affective valence and arousal [94].

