The smartphone-delivered ABM and sham training (Figure 4) will both involve the same MDP task timing, scoring, and monetary reinforcement schedule as the laboratory AB assessment, with several exceptions. First, the ratio of probes following each picture type will differ by ABM group. In the ABM group, 100% of the probes will replace neutral pictures, to reduce participants' AB to smoking cues, while in the sham group, probes will follow each of the 2 picture types an equal number of times, to avoid influencing AB. Second, the training groups will both involve more blocks of trials than the AB assessment, consistent with other ABM studies [2]. The ABM training session will consist of 22 picture pairs repeated 20 times over 8 blocks, for a total of 440 trials, 55 per block. Third, the task will be presented over the smartphone, with no EEG collected. Each picture will be 5 cm wide by 5 cm high, and the response will be considered correct if the participant taps within this region on the side of the screen where the probe is presented. The maximum performance bonus for the MDP task for each session is \$11 (\$0.025 per trial). The in-home ABM training will last for approximately 20 min.

[figure not shown]
In-Home Smartphone: AB assessment using the Stroop. After completing the last block of ABM or sham training, participants will immediately and seamlessly transition to the in-home AB assessment component. The in-home AB assessment will use the Stroop task. The in-home Stroop task will be identical to the laboratory task, except that it will be given over the smartphone. Thus, the 4 response buttons will be presented on the touch screen, 2 each to the left and right of the word (**Figure 5**). The placement of the buttons on the left and right side of the screen will allow for participants to respond quickly with their thumbs. The color assigned to each of the four buttons will be randomly varied from day to day. The word will be presented in the center of the screen, approximately 4 cm wide and 2 cm high. Each button will be 3 cm wide by 3 cm high. The in-home AB assessment will take approximately 7 min to complete. The maximum performance bonus for the Stroop task for each session is \$4 (\$0.025 per trial).

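### The dot-probe bias score accepts presses from 20 ms after the probe, too early to be reactions to it; if ABM participants anticipate the neutral side, this could imitate the Aim 1 training effect

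*Combined protocol and SAP*

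**What the plan says.** All references are to the combined protocol and SAP. In *Laboratory sessions: AB assessment using the MDP task*, error feedback follows "Incorrect responses, or responses that occur outside of 20-1000 ms interval after probe onset". The score uses the same window: "An AB score will be calculated by taking the mean RT difference between the CIG and NEU targets on trials with correct responses", limited to responses inside it. No other lower limit, anticipation rule or outlier trimming appears.

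On the task itself, the same section says: "The laboratory AB assessment will consist of 16 picture pairs repeated 10 times over four blocks, for a total of 160 trials", with "random probes following each picture or word an equal number of times". The response is a choice of side: "Participants will be instructed to press a button corresponding to the side of the screen (left or right) where the probe appears". The pictures are shown for 200 ms before the probe.

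Under *ERP measure changes in AB*, the P1 is described as "peaking within 90 to 160 ms from visual stimulus onset".

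Under *In-Home Smartphone*, training shares the laboratory task's timing, scoring and payment, but the arms differ: "In the ABM group, 100% of the probes will replace neutral pictures", while sham probes are split equally. *Statistical Approach & Expected Outcomes* makes the neutral minus cigarette RT difference the Aim 1 measure and predicts a fall in the ABM arm but not in sham. Awareness of the contingency is examined only in the exploratory analyses.

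**The concern.** An RT bias score has meaning only if each RT is a reaction to the probe. By the protocol's own figure, the early visual response peaks no sooner than 90 ms after onset, and a choice and a movement must still follow. Presses at 20 to 90 ms were therefore set in motion before the probe could have been used, yet the scoring rule keeps them when they happen to be correct.

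Guesses with no side preference would add noise and cancel in the difference. The arms, however, are trained on different contingencies. A neutral-side press is always right in ABM training and right half the time in sham. If that habit carries into the laboratory, correct-only scoring treats the two probe types unequally: the early neutral-side press survives on neutral-probe trials and disappears on smoking-probe trials. Only the neutral mean falls. At stake is the within-modality Aim 1 outcome, where such an artefact would run in the predicted direction without any change in attention.

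**Working it through.** **1. The plan's own figure.** The power analysis gives a detectable interaction of Cohen's f = 0.11 (N = 250, alpha 0.01, r = 0.5, epsilon = 0.75, 2 groups, 3 sessions).
- Noncentrality = f² × N × 3 × epsilon / (1 − r) = 0.0121 × 250 × 3 × 0.75 / 0.5 = 13.6.
- Degrees of freedom are 2 × 0.75 = 1.5 and 248 × 2 × 0.75 = 372. Power is 0.821.
- With 30% attrition (N = 175) and f = 0.13, power is 0.808. Both figures reproduce.

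For a group difference d that is equal at both post-training sessions, f = d / (s√18), so f = 0.11 means d = 0.467 × s, where s is the SD of the AB score. The documents give no SD for the MDP score. For assumed values of 15, 20 and 30 ms, d is 7.0, 9.3 and 14.0 ms.

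**2. Counts and timing.** 16 × 10 = 160 trials, 80 per probe type. Guessing on 2% or 5% of trials is 1.6 or 4 trials per probe type. Training comprises 22 × 20 = 440 trials over 13 days, or 5,720. A press 20 to 90 ms after the probe comes 220 to 290 ms after picture onset.

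**3. Shift in the AB score with no true attentional effect.** Assumptions not in the documents: genuine RT mean 350 ms; guesses spread evenly over 20 to 150 ms (mean 85 ms); a share g of trials guessed; a share q of guesses to the neutral side. Accuracy on genuine responses is taken as 96%, the figure the protocol reports from an at-home study.

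Mean RT for a probe type = [g·c·85 + (1 − g)·0.96·350] / [g·c + (1 − g)·0.96], with c = q for neutral probes and c = 1 − q for smoking probes.

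Example, g = 5%, q = 1: neutral mean = (4.25 + 319.2) / 0.962 = 336.2 ms; smoking mean = 350 ms; shift = −13.8 ms.

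| Share to neutral side (q) | g = 0 | g = 2% | g = 5% |
|---|---|---|---|
| 0.5 (no preference) | 0 | 0 | 0 |
| 0.75 | 0 | −2.8 ms | −6.9 ms |
| 1 (worst case) | 0 | −5.5 ms | −13.8 ms |

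At q = 1 and genuine means of 300 to 400 ms, the shift is −4.5 to −6.6 ms at 2% and −11.2 to −16.4 ms at 5%.

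**4. A cruder worst case.** If all guesses go to the neutral side at about 55 ms and the mean RT is 400 ms, the shift is about g × (400 − 55): 0.02 × 345 = 6.9 ms and 0.05 × 345 = 17.25 ms. With a mean RT of 500 ms these become 8.9 and 22 ms. The rounded worst-case range of 6 to 17 ms therefore belongs to mean RTs of 350 to 400 ms.

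**5. Effect on the test.** With 125 per arm and r = 0.5, the SD of change equals s, so the noncentrality is shift / (s√(2/125)). At alpha 0.01, a spurious shift of 2.7 ms is declared significant with probability 0.12, 0.065 or 0.03 for s = 15, 20 or 30 ms. For 5.5 ms the probabilities are 0.62, 0.34 and 0.13.

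**6. Effect of a later floor.** At q = 1, a 100 ms floor cuts the shifts to −1.8 and −4.6 ms at 2% and 5%. A 150 ms floor removes them, but only because guesses were assumed to end at 150 ms.

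**The case against.** The mechanism is conditional. The documents do not show that anyone guesses, that the contingency is learned, or that it carries over; the protocol treats awareness as an open question. Payment is a flat $0.025 for any correct response inside the window, so a very fast press earns no more than a slow one, although instructions mention both accuracy and speed. In the laboratory a neutral-side guess is wrong half the time, forfeits the payment and brings a 2000 ms error screen. This discourages guessing and stands as a limit on size.

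Timing is a second limit. Suppose picture-driven presses average 400 ms from picture onset with SD 80 ms, that is, 200 ms after the probe. About 7% would then fall at 20 to 90 ms and about 69% beyond 160 ms (45% to 96% for means of 350 to 500 ms). A later floor would not catch most of them. This also stands, and is why rates by arm are needed besides the floor.

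Three stronger readings are tempting but unsupported:
- A reader might infer that the score is biased towards ABM. The documents show only that it could be.
- A reader might divide 17.25 ms by the 46.6 ms SD in *Preliminary Studies* and report 0.37 SD. That SD comes from a hand-held Stroop task and says nothing about the laboratory MDP.
- A reader might treat 160 ms as a proven minimum, or 20 as a slip for another value. The P1 range is a peak latency, not a motor limit, and nothing in the text shows a typing error.

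The planned eye-tracking, ERP and awareness analyses add context but remove no trial from the Aim 1 score.

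**Conclusion.** The point holds in a limited form. The stated window admits presses that cannot be reactions to the probe, and no other rule removes them. If neutral-side anticipations occur in the ABM arm after training, the direction follows from the different training contingencies and correct-only scoring: neutral minus cigarette RT falls in that arm alone.

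The documents do not fix the size. It is zero without guessing or without carry-over. Under assumed guess rates of 2 to 5% it is roughly 3 to 7 ms with 75% of guesses to the neutral side, and 6 to 17 ms as a worst case with all of them. Guess rate, guess time, side preference and mean RT are all assumptions. Only the MDP score is concerned; the Stroop score and the smoking outcomes are not affected. This is a cheap improvement, not evidence that the Aim 1 comparison is invalid.

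**What to change.** - Pre-specify a later lower bound for scoring the MDP. The end of the protocol's P1 range, 160 ms, is a reasonable example. If 20 is a typing error, correct it.
- Apply the bound offline and identically to all three laboratory sessions and both arms. On-screen feedback and payment need not change.
- Repeat the Aim 1 MDP analysis across several cut-offs.
- Report, by arm, session and probe type, the rate of responses below the bound and the error rate. Slower contingency-driven guesses pass any such floor, but they would show as excess errors on smoking-probe trials in the ABM arm after training.

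The cost is a small number of lost trials and a few lines of scoring code, provided that trial-level RTs and responses are kept. No visit or task changes.
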